### Number of Patients:

Twenty-five evaluable patients were enrolled in Part 1 (dose escalation).

In Part 2, the first expansion cohort (“all-comers”) 23 unselected relapsed or refractory AML patients have been enrolled. An additional expansion cohort (“IDH mutants”) will enroll approximately 20 relapsed or refractory AML patients harboring an IDH mutation (either IDH1 or IDH2).

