**Table 2: Part 2 Study Objectives and Endpoint (Assessment)**

Objective	Endpoint (Assessments)
Primary:	

 
To further characterize the safety profile of single agent SEL24/MEN1703
 
	
 
The number and frequency of AE, safety laboratory, vital signs and ECG assessments
 

Secondary:	

 
To assess anti-leukemic activity of single agent SEL24/MEN1703
 
	
 
Assessment of bone marrow and peripheral blast % and other assessments of clinical benefit including ORR (CR, CRi, CRh and MLFS), PR rate, DoR, RFS, EFS, OS, transfusion conversion rate, transfusion maintenance rate, HSCT rate
 

 
To evaluate the PK profile of SEL24/MEN1703 and its metabolites, as appropriate
 
	
 
Assessment of PK variables, including <math>C_{max}</math>, AUC and <math>t_{1/2}</math>
 

Exploratory:	

 
To assess the PD activity of SEL24/MEN1703
 
To assess the genetic profile of AML cells
 
	
 
Flow cytometry assessment of relevant biomarkers (e.g. pS6)
 
Analysis of relevant mutations in peripheral blasts and bone marrow by using Next Generation Sequencing and/or qRT-PCR
 

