***Allogeneic hematopoietic stem cell transplant (HSCT) rate***

Allogeneic HSCT rate is defined as the percentage of subjects undergoing allo-SCT during the study period. MRD status will be recorded immediately prior to the transplant and after the procedure whenever a bone marrow aspirate/biopsy will be collected (recommended every 2 months unless differently indicated by the treating physician based on actual patient's parameters).

In the event a patient undergoes allogeneic HSCT, the following information will be recorded: a) date of transplant; b) HLA match type (HLA-identical sibling, syngeneic, HLA-matched other relative, HLA-

mismatched relative, Unrelated donor); c) source of stem cells (Bone marrow, peripheral blood, cord blood, others); d) conditioning regimen (myeloablative, non-myeloablative).

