**Table 2: Part 2 Study Objectives and Endpoint (Assessment)**

Objective	Endpoint (Assessments)
Primary:	

 
To further characterize the safety profile of single agent SEL24/MEN1703
 
	
 
The number and frequency of AE, safety laboratory, vital signs and ECG assessments
 

Secondary:	

 
To assess anti-leukemic activity of single agent SEL24/MEN1703
 
To evaluate the PK profile of SEL24/MEN1703 and its metabolites, as appropriate
 
	
 
Assessment of bone marrow and peripheral blast % and other assessments of clinical benefit including ORR (CR, CRi, CRh and MLFS), PR rate, DoR, RFS, EFS, OS, transfusion conversion rate, transfusion maintenance rate, HSCT rate
 
Assessment of PK variables, including <math>C_{max}</math>, AUC and <math>t_{1/2}</math>
 

Exploratory:	

 
To assess the PD activity of SEL24/MEN1703
 
	
 
Flow cytometry assessment of relevant biomarkers (e.g. pS6)
 

Objective	Endpoint (Assessments)

• To assess the genetic profile of AML cells

	

• Analysis of relevant mutations in peripheral blasts and bone marrow by using Next Generation Sequencing and/or qRT-PCR

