## 8.9. Methods for Assessment of Anti-Leukemic Activity

No formal statistical analysis will be performed on anti-leukemic parameters.

Anti-leukemic activity data will be collected throughout Part 1 and Part 2 and will be summarized by cohort, by dose and overall. In Part 2 response may be summarized and an exact 95% confidence interval (CI) calculated.

Measures of anti-leukemic activity will include:

- Changes in pre- and post-treatment levels of leukemic blasts in the peripheral blood and/or bone marrow;
- Duration of response (DoR);
- Relapse-free survival (RFS);
- Event-free survival (EFS);
- Overall Survival (OS)
- Transfusion conversion rate;
- Transfusion maintenance rate;
- HSCT rate.

Where possible disease assessment will be evaluated according to the response criteria in AML. (see [Appendix D](#)).

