5.4.2. Secondary endpoints

Study Part 1:

- The number and frequency of AEs, safety laboratory, vital signs and ECG assessments

Study Part 1 and 2:

- Disease assessment will involve evaluation of leukemic blast proportion in the bone marrow. Hematologic parameters from the routine local assessments including blast percentage (where applicable), platelet count, and other relevant parameters such as transfusion dependence will also contribute to this assessment. Disease assessment will also include an aliquot of bone marrow aspirate/biopsy that will be centrally stored for future analysis (e.g. minimal residual disease), if any.
- Overall response rate (ORR), defined as the proportion of patients who have a complete remission (CR), complete remission with incomplete hematologic recovery (CRI), complete remission with partial hematologic recovery (CRh) or morphologic leukemia-free state (MLFS) response to therapy.
- Partial remission (PR) rate, defined as the proportion of patients who have a partial remission response to therapy.
- Duration of response (DoR), defined as the time from the date of first CR, CRI, CRh, CRMRD-, MLFS or PR until the date of documented relapse of any type, progressive disease or death due to disease progression for subjects who achieve CR, CRI, CRh, CRMRD-, MLFS or PR. Subjects who either do not relapse or die without report of relapse are considered nonevents and censored at their last relapse-free disease assessment date. Subjects who undergo an allogeneic HSCT will be considered non events and censored at the time of HSCT

- Relapse free survival (RFS), defined as the time from the date of first CR, CRi, CRh or CRM RD- until the date of documented relapse or death from any cause. Subjects who either do not relapse or do not die are censored at their last relapse-free disease assessment date.
- Event free survival (EFS), defined as the time from the date of first study drug intake until the date of documented relapse, treatment failure or death from any cause. For a subject who did not experience the event, EFS is censored at the date of last relapse-free disease assessment. Subject is not censored at HSCT.
- Overall survival (OS), defined as the number of days between the first study drug administration and death from any cause. Patients without the event are censored at the last date of follow-up.

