- Evaluation of CYP2D6 phenotyping will be carried out. As SEL24/MEN1703 may both inhibit and act as a substrate for Cytochrome P450 enzyme CYP2D6, patients will be assessed for their CYP2D6 phenotype. A blood sample collected during Screening will be used for this assessment and results will be reported separately.

Study Part 2:

- Transfusion conversion rate, defined as the number of subjects who were transfusion dependent at baseline period but become transfusion independent at post-baseline period divided by the total number of subjects who were transfusion dependent at baseline period.
- Transfusion maintenance rate, defined as the number of subjects who were transfusion independent at baseline period and still maintain transfusion independent at post-baseline period divided by the total number of subjects who were transfusion independent at baseline period.
- Allogeneic HSCT rate, defined as the percentage of subjects undergoing allo-HSCT during the study period.

Both transfusion conversion rate and maintenance rate apply to subjects who have evaluable post-baseline transfusion status.

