- Relapse-free survival (RFS);
- Event-free survival (EFS);
- Overall Survival (OS);
- Transfusion conversion rate;
- Transfusion maintenance rate;
- HSCT rate.

OS, RFS, EFS rates at specific timepoints (e.g. 6, 12 months) may also be performed with exploratory intent.

Transfusion conversion rate, transfusion maintenance rate and HSCT rate will be evaluated only in the IDH-mutants cohort.

Where possible disease assessment will be evaluated according to the response criteria in AML6 (Appendix D of Study Protocol). Efficacy analyses will be performed through descriptive statistics.

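### SAP 12.1 limits the HSCT rate to the IDH-mutants cohort, leaving a Part 2 secondary endpoint unreported for 23 of about 43 patients with no declared departure from the protocol

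*SAP*

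**What the plan says.** **Endpoint definition.** Protocol Table 2 includes, among the Part 2 secondary measures, "OS, transfusion conversion rate, transfusion maintenance rate, HSCT rate". The protocol synopsis defines the last of these: "Allogeneic HSCT rate is defined as the percentage of subjects undergoing allo-SCT during the study period". SAP 5.4.2 repeats the definition under its Part 2 heading: "Allogeneic HSCT rate, defined as the percentage of subjects undergoing allo-HSCT during the study period". None of these places names a cohort. Part 2 consists of the all-comers and IDH-mutants cohorts (protocol 4.2, SAP 5.1).

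**Reporting rule.** Protocol 8.9 says: "Anti-leukemic activity data will be collected throughout Part 1 and Part 2 and will be summarized by cohort, by dose and overall". HSCT rate is in the list of measures that follows. SAP 12.1 carries the same rule and the same item, and has the measures computed on both the safety and the efficacy populations.

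**Restriction.** After that list, SAP 12.1 adds: "Transfusion conversion rate, transfusion maintenance rate and HSCT rate will be evaluated only in the IDH-mutants cohort".

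**Declared changes.** SAP 3.1 states that the analyses follow the protocol and its amendments. It does not mention the restriction.

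**The concern.** A protocol secondary endpoint is narrowed in one sentence of the SAP's efficacy section. That sentence conflicts with the protocol, with SAP 5.4.2, and with the reporting rule earlier in SAP 12.1. A programmer following 12.1 would produce no HSCT rate for the all-comers cohort, and a reader relying on 3.1 would not know that anything had been left out.

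For the two transfusion rates the protocol supplies a ground. The synopsis says transfusion dependency is collected from V12.0, and by then all-comers enrolment was complete. The HSCT definition comes directly after that text and has no such clause. The transplant provisions in protocol 4.2 are also written for Part 2 subjects generally.

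At stake is completeness of reporting: whether any all-comer went on to transplant, or none did, would not appear as a rate.

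**Working it through.** **1. Check the head counts.** The study has no formal sample size calculation, so the figures to reproduce are counts.
- SAP Section 8 plans approximately 65 evaluable patients: 25 (Part 1) + 20 (all-comers) + 20 (IDH mutants) = 65. This agrees.
- Protocol 1.4 gives 48 patients dosed and 30 at 125 mg: 25 + 23 = 48 and 7 + 23 = 30. Both agree.

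**2. Part 2 denominator.**
- All-comers: the protocol synopsis reports "23 unselected relapsed or refractory AML patients have been enrolled". SAP Section 8 also has 23 treated, which is 20 planned plus 3 replacements.
- IDH mutants: approximately 20 planned.
- Part 2 total: 23 + 20 = about 43.

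**3. Share left out by SAP 12.1.** 23 / 43 = 53.5%. The IDH figure is approximate. If that cohort ends at 18 to 22 patients (an assumed range), the share is 23/41 = 56.1% to 23/45 = 51.1%.

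**4. Does the documented reason cover HSCT?**

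| Item | Transfusion rates | HSCT rate |
|---|---|---|
| Part 2 endpoint without cohort limit (protocol Table 2, SAP 5.4.2) | Yes | Yes |
| In the list to be reported for each cohort and in total (protocol 8.9, SAP 12.1) | Yes | Yes |
| Start of collection tied to V12.0 (protocol synopsis) | Yes | Not stated |
| Restricted to IDH mutants (SAP 12.1) | Yes | Yes |
| Restriction declared in SAP 3.1 | No | No |

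**5. Is HSCT information expected outside the IDH cohort?**
- In SAP 5.4.2, under the heading covering both Parts, the DoR rule reads: "Subjects who undergo an allogeneic HSCT will be considered non events and censored at the time of HSCT". This presupposes transplant dates for responders in every cohort.
- SAP 11.4 summarises prior and concomitant procedures on the whole safety population.

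So the SAP expects some transplant information for all-comers. Neither text shows that it is complete.

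**6. Illustration of the denominator.** For 0 transplants in n patients, the exact two-sided 95% upper limit is 1 − 0.025^(1/n):
- n = 20: 16.8%
- n = 43: 8.2%

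Zero transplants is an assumption, and no interval is planned for this rate. The limits show only what a Part 2 total would add. The IDH-cohort rate is the same with or without the restriction.

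**The case against.** The strongest defence is that all three endpoints were treated alike for one reason. They appear together as Part 2 measures and are absent from the Part 1 table. The HSCT recording text is prospective and directly follows the V12.0 transfusion text, and V12.0 notes that the all-comers cohort was already complete. On this view 12.1 is a specific rule narrowing a general list, and the only fault is that it was not declared. The documents neither confirm nor exclude that reason, because they do not say when HSCT capture began. A rate of x/23 from incomplete capture would be biased towards zero, and a narrow pooled limit would be false precision. That part of the objection stands and shapes the fix.

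A reader might infer more than the documents support:

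- **That complete transplant data exist for all-comers.** Footnote 18 to protocol Table 5 covers AML-related medications at follow-up and does not name transplants. The SAP's version of that footnote omits even the medications. The DoR rule needs dates only for responders, and the DoR censoring rules in SAP 11.3 and 12.1 do not repeat it.
- **That a planned comparison is lost.** The protocol plans separate descriptive analysis of the two cohorts and allows pooling. No between-cohort test is planned. The activity contrast it wants to explore is between IDH-inhibitor pre-treated and naïve patients.
- **That the reported rate would be wrong.** Two transplants, both in the IDH cohort, would give 2/20 = 10.0% there and 2/43 = 4.7% for Part 2. These are different quantities in an assumed scenario, and the first is correct for its cohort.

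What does not stand is leaving the text as it is. Even if the restriction is justified, it contradicts 5.4.2 and is missing from 3.1.

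**Conclusion.** The point holds as an undeclared narrowing of a protocol secondary endpoint. Under SAP 12.1 as written, the HSCT rate is not reported for 23 of about 43 Part 2 patients (53%; 51% to 56% if the IDH cohort ends at 22 to 18). The V12.0 clause accounts for the transfusion rates only.

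The conclusion rests on two readings. An unrestricted Part 2 endpoint is taken to apply to both Part 2 cohorts, which the reporting rule in protocol 8.9 and SAP 12.1 supports, although no text uses those words. The 43 combines actual enrolment in one cohort with an approximate plan in the other.

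The documents do not show that the restriction is unjustified, nor that all-comers transplant data are complete. The consequence is limited to descriptive reporting. The change should be made, but no decision rule, test or sample size turns on it.

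**What to change.** 1. In SAP 12.1, take HSCT rate out of the restricting sentence. Report it for each Part 2 cohort and for Part 2 overall, on the safety and efficacy populations, using the HSCT dates needed for DoR censoring together with recorded concomitant procedures.
2. Add a footnote on any less complete capture in all-comers before V12.0.
3. Keep the restriction for the two transfusion rates, and state it with its reason in SAP 5.4.2 and 3.1.
4. First confirm how transplants were captured in all-comers. If capture was not systematic, list the known transplants without a rate, and declare that restriction and its reason in SAP 3.1.

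The cost is SAP wording, HSCT entries by cohort and overall in Table 3.2 (no table title in SAP 13.2.1 names the HSCT rate), and a check of how procedures were recorded for 23 patients. No further patients or tests are needed.

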12.2. Subgroup analyses

Not applicable.

12.3. Pharmacokinetic analysis

The PK analysis will be run on the PK population.

Plasma concentration values Below the Lower Limit Of Quantification (BLLOQ) will be set to zero before the t_{max} and to “missing” after the t_{max} . Plasma concentrations reported as $>$ BLLOQ at time zero, when the subject has not previously been dosed, will be set to their real value. Data-replacements will be implemented by the Global Clinical Pharmacology and Pharmacometrics department. A footnote should be added to the listing, tables, and figures, in order to indicate the LOQ value.

If actual sampling time is missing, the nominal time will be used.

If the 24-hours post dose sample is collected after the intake of the following dose, the corresponding concentration will be reported in the listing with a FLAG and excluded from the PK parameter calculation.

If urine volume is missing, concentrations will be reported in the listing and no PK parameters will be calculated.

If samples are collected during an unscheduled visit, individual concentrations and PK parameter will be reported in the listing with a FLAG, but they will be excluded from the summary statistics.

All PK plasma and urine concentrations and PK parameters will be summarized by cohort, cycle, day, IDH mutational status, and nominal time point, and by dose, cycle, day, IDH mutational status and nominal time point, by using the following descriptive statistics:

- Number of non-missing observations (N),
- Arithmetic mean (AM) and its 90% confidence interval (CI), standard deviation (SD), coefficient of variation (CV%) and standard error (SE),
- Geometric mean (GM) and its 90% CI and GM CV%,
- Median,
- Minimum (min) and maximum (max).

Individual plasma concentration data versus time will be presented in a data listing and visualized as individual concentration-time plots. Individual urine concentration data will be presented in a data listing.

Actual times will be used for calculation of PK parameters and replaced by nominal times when missing. Plot of individual and aggregated concentration versus time curves will be generated with nominal times.

13. Tables, listings and figures

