#### **5.3.15. CYP2D6 phenotyping**

As SEL24/MEN1703 may both inhibit and act as a substrate for Cytochrome P450 enzyme CYP2D6, patients will be assessed for their CYP2D6 phenotype. A blood sample collected during Screening will be used for this assessment.

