No recruitment interval was applied in the cohort 4F where formulated SEL24/MEN1703 IMP was introduced, as this dose level had already been explored with the non-formulated SEL24/MEN1703 API in capsules. Upon the successful completion of the repeat cohort with the formulated IMP, the study progressed to the next Cohort 4b and onwards, according to the study design, using SEL24/MEN1703 formulated IMP only. In particular, it was shown that, overall, PK disposition of SEL24/MEN1703 (absorption, distribution and elimination) following the administration of formulated IMP is in line with that observed with non-formulated IMP. This evidence further supports that no dose adjustment is warranted with formulated IMP.

Patients who commenced dosing with the non-formulated SEL24/MEN1703 API in capsules and who were still on treatment, continued receiving this formulation until treatment withdrawal per protocol.

Subsequently, a protocol amendment was implemented to treat up to 4 additional patients at 150 mg under Bayesian modified toxicity probability interval (mTPI) approach, with a target toxicity rate of $\leq 25\%$. The first patient treated under his protocol at 150 mg dose level experienced a DLT. As a consequence, the recruitment was stopped and the recommended dose (RD) for next development steps was determined at 125 mg.

Recruitment and dose escalation for each cohort in Part 1 is described in Table 1.

Table 1: Patients exposure along Dose Escalation Steps

Cohort	Dose Level	Patients treated with non-formulated IMP	Patients treated with Formulated IMP	Patients who experienced DLT
1	25 mg	2*	0	1
2	50 mg	3	0	0
3	75 mg	3	0	0
4	100 mg	3	0	0
4F	100 mg	0	3	0

4b	125 mg	0	7*	1
5	150 mg	3	0	2
5F	150 mg	0	1	1

*One patient not DLT evaluable

In Part 1, according to a 3+3 design, the MTD is defined as the highest dose at which no more than 1 in up to 6 patients experience a DLT during Cycle 1. In Cohort 5, up to 4 additional patients could have been treated at 150 mg formulated IMP according to a Bayesian modified toxicity probability interval (mTPI) with a target toxicity rate $\leq 25\%$. In case none of these 4 patients experienced a DLT, higher dose levels may have been considered.

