7.4.2. Protocol Deviations and Data Review Meeting

Categories of protocol violations will be defined and will be integrated in the statistical analysis.

During the Data Review Meeting that will take place at the end of the study, the final list of Protocol Deviations will be defined. (Please refer to MedPace Protocol Deviation Plan V3.0 of 04 November 2021 for the full deviation categories list).

8. Determination of sample size

Due to the nature of the study, no formal sample size calculation is applicable. However, under Protocol Version 12.0, approximately 65 evaluable patients with AML were planned to be enrolled in this study, with 20 of them to be enrolled in the all-comers cohort and 20 in the IDH-mutants cohort (Part 2).

The study Part 1 was initially designed with an accelerated titration design for the first 4 cohorts, then a 3+3 design had to be followed from the former fifth cohort (150 mg dose level) onwards.

However, following the occurrence of 2 DLTs at the 150 mg dose level, one of which resulted in a fatal treatment-related outcome, the study design was revised to follow a 3+3 design from Cohort 2 onwards in order to assess for DLT, adverse events, and adequate PK profile data from at least 3 patients in each dose level from 50 mg onwards.

The final number of patients treated in Part 1 was 25 and 125 mg was considered the RP2D.

This cohort was then expanded to enroll 20 additional patients. Nevertheless, 3 patients were replaced and a total number of 23 patients were treated in this study phase. The replacement occurred when patients were not considered evaluable for safety and/or lacked one post-treatment bone marrow disease assessment.

9. Randomization Methodology

The study is non randomized.

10. Stopping Rules and Blinding

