Efficacy Tables (to be performed on both efficacy population as well as safety population)

Table 3.1: Summary of Tumor Response by Visit
 Table 3.2: Summary of Tumor Response Endpoints
 Table 3.3: Summary of Time to Event Endpoints

PK Tables

Table 4.1: Summary statistics of MEN1703 PK concentration in plasma by cohort, cycle, day, IDH mutational status and nominal time point, and by dose, cycle, day, IDH mutational status and nominal time point
 Table 4.2: Summary statistics of MEN1703 PK parameters by cohort, cycle, day, IDH mutational status and nominal time point, and by dose, cycle, day, IDH mutational status and nominal time point.
 Table 4.3: Summary statistics of MEN1703 PK concentration in urine by cohort, cycle, day, IDH mutational status and nominal time point, and by dose, cycle, day, IDH mutational status and nominal time point
 Table 4.4: Summary statistics of MEN1703 urinary PK parameters by cohort, cycle, day, IDH mutational status and nominal time point, and by dose, cycle, day, IDH mutational status and nominal time point
 Table 4.5: Summary statistics of MET3 PK concentration in plasma by cohort, cycle, day, IDH mutational status and nominal time point, and by dose, cycle, day, IDH mutational status and nominal time point
 Table 4.6: Summary statistics of MET3 PK parameters by cohort, cycle, day, IDH mutational status and nominal time point, and by dose, cycle, day, IDH mutational status and nominal time point.

Table 4.7: Summary statistics of MET3 PK concentration in urine by cohort, cycle, day, IDH mutational status and nominal time point, and by dose, cycle, day, IDH mutational status and nominal time point

Table 4.8: Summary statistics of MET3 urinary PK parameters by cohort, cycle, day, IDH mutational status and nominal time point, and by dose, cycle, day, IDH mutational status and nominal time point

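### All eight PK summary tables are crossed with IDH status: no table summarises a whole cohort or dose level, and a three-patient cohort of mixed status would fall to cells of two and one

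*SAP*

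**What the plan says.** SAP section 12.3 sets out two summaries of all plasma and urine concentrations and parameters. One is "by cohort, cycle, day, IDH mutational status, and nominal time point". The other is "by dose, cycle, day, IDH mutational status and nominal time point, by using the following descriptive statistics". Each cell is to carry N, the arithmetic mean with 90% CI, SD, CV% and SE, the "Geometric mean (GM) and its 90% CI and GM CV"%, the median and the range.

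The table index in SAP section 13.2.1 follows suit. A typical title begins "Table 4.2: Summary statistics of MEN1703 PK parameters by cohort, cycle, day, IDH mutational status and nominal time point" and goes on to the second form, "by dose, cycle, day, IDH mutational status and nominal time point". All eight PK tables, for parent drug and metabolite, in plasma and urine, have this structure.

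The default in SAP section 11.2 is presentation by cohort, dose and overall, but it gives way wherever another layout is specified, and section 12.3 specifies one. The PK figures carry no stated IDH split: Figures 22 and 25 show mean profiles, and Figures 23 and 26 are boxplots of Cmax and AUC24 against dose. Individual values are in Listings 4.24 to 4.31.

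**The concern.** The PK profile is a secondary objective in both parts of the study. SAP section 5.1 also says that the move to a 3+3 design from 50 mg upwards was made partly to obtain PK profiles from at least three patients per dose level. A split by IDH status, a tumour marker for which neither document gives a pharmacokinetic rationale, can undo that minimum in the tables that report it.

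What is at stake is the readability and precision of the numerical PK results. A reader who wants the geometric mean AUC with its interval at 75 mg, or at 100 mg over both formulations, would not find it in any planned table unless every patient there happened to share the same IDH status. In the by-cohort tables the split also adds nothing for the Part 2 IDH-mutant cohort, because inclusion criterion 1 requires the mutation. Urine was collected in Part 1 only, so the four urine tables (4.3, 4.4, 4.7 and 4.8) would divide only the small escalation cohorts.

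**Working it through.** **1. Cohort sizes.** SAP Table 1 ("Patients exposure along Dose Escalation Steps") gives 2 at 25 mg, 3 at 50 mg, 3 at 75 mg, 3 in Cohort 4, 3 in Cohort 4F, 7 in Cohort 4b, 3 in Cohort 5 and 1 in Cohort 5F. The sum is 2 + 3 + 3 + 3 + 3 + 7 + 3 + 1 = 25. This agrees with SAP section 8: "The final number of patients treated in Part 1 was 25". Five cohorts (2, 3, 4, 4F and 5) have exactly three patients.

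**2. What a split does to the interval.** The half-width of a 90% CI for a mean, in SD units, is t(0.95, n − 1)/√n.

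- n = 1: no SD, SE, CV% or CI can be computed.
- n = 2: 6.314/√2 = 4.46.
- n = 3: 2.920/√3 = 1.69.
- n = 6 (100 mg, Cohorts 4 and 4F together): 2.015/√6 = 0.82.

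The ratio for n = 2 against n = 3 is 4.46/1.69 = 2.6.

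For the geometric mean, the interval multiplies and divides the estimate by exp(s × half-width), where s = √ln(1 + CV²). The documents give no between-patient CV, so these values are assumptions:

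| Assumed CV | Factor at n = 2 | Factor at n = 3 |
|---|---|---|
| 30% | 3.71 | 1.64 |
| 50% | 8.24 | 2.22 |
| 80% | 23.11 | 3.27 |

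**3. How often a three-patient cohort would split.** With an IDH-mutant share p and independent patients, a cohort of three holds both types with probability m = 1 − p³ − (1 − p)³. At least one of the five is mixed with probability 1 − (1 − m)⁵. The documents give no value of p for Part 1, so p is also an assumption.

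| p | p³ | (1 − p)³ | m | At least one of five | All five |
|---|---|---|---|---|---|
| 15% | 0.003 | 0.614 | 0.38 | 0.91 | 0.008 |
| 20% | 0.008 | 0.512 | 0.48 | 0.96 | 0.025 |
| 30% | 0.027 | 0.343 | 0.63 | 0.99 | 0.099 |

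Over a wider range of 10% to 50%, m runs from 0.27 to 0.75.

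**4. What removing the split gives.** Each of the five cohorts becomes one cell of 3. By dose, the Part 1 cells are 2, 3, 3, 6, 7 and 4 at 25, 50, 75, 100, 125 and 150 mg. Part 2 adds the 23 all-comers and the planned 20 or so IDH-mutant patients at 125 mg.

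**The case against.** Several points can fairly be made for the plan.

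- **The figures give an unsplit view.** The boxplots cover the main exposure parameters on Cycle 1 Days 1 and 14 against dose, and the listings hold every value. This stands. A reader might infer that PK by dose will not be visible at all, and the documents do not support that. What is missing is narrower: the tabulated means, intervals and CVs for whole groups.
- **Small cells are not certain.** A cohort of uniform IDH status keeps its three patients. This also stands. It would be wrong to read the plan as breaking up every three-patient cohort: even at an assumed 30% share, all five are mixed only about 10% of the time.
- **Three patients are few in any case.** An interval of ±1.69 SD is already wide, the analysis is descriptive, and the recommended dose has been set. This limits the importance of the point, but it does not justify a layout that can make the interval wider or impossible to compute.
- **IDH status is a design factor in Part 2.** That supports a split at 125 mg. It does not support one at 50, 75, 100 or 150 mg.
- **The index is indicative.** SAP section 13.1 leaves the final output list to agreement with the Study Physician, so unsplit tables could still appear. But section 12.3 itself prescribes the split.

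A reader might also infer that CYP2D6 phenotype is collected and then ignored. Protocol section 5.3.15 gives the reason for collecting it: "As SEL24/MEN1703 may both inhibit and act as a substrate for Cytochrome P450 enzyme CYP2D6". No PK table in the SAP uses it. However, protocol section 5.3.14 and SAP section 5.4.2 both say that these results will be reported separately, so their absence from the tables is not a defect. Nor do the documents show that CYP2D6 is the main determinant of exposure: they say only that the drug may be a substrate, and they name BCRP as well.

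**Conclusion.** The point holds as a matter of table layout. Every planned numerical PK summary is crossed with IDH status, and none is specified for a whole cohort or dose level. In any three-patient cohort of mixed status, the required 90% CI is 2.6 times wider in SD units in the cell of two and cannot be computed in the cell of one. At 100 mg, the by-dose table would give up a single cell of six, with a half-width of 0.82 SD, if those six patients were mixed.

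The interval widths follow from the t distribution and the cohort sizes alone. The probability of a split (38% to 63% for a given three-patient cohort) rests on an assumed mutant share of 15% to 30% and on independence between patients; actual Part 1 status would replace it. No safety conclusion or dose decision is shown to depend on this, so it is a cheap improvement and not an error that threatens the trial.

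**What to change.** In SAP section 12.3 and the titles of Tables 4.1 to 4.8, make the main summaries by cohort, cycle, day and nominal time, and by dose, cycle, day and nominal time, without IDH status. Add IDH status as a supplementary split at 125 mg only. This is useful mainly for the plasma tables (4.1, 4.2, 4.5 and 4.6): with urine collected in Part 1 only, at most the seven Cohort 4b patients could contribute to a urine split at that dose.

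The cost is a change of by-variables and a few added or re-specified tables, from data already held. As an optional clarification, one sentence in the SAP could say whether the separate CYP2D6 report will relate phenotype to exposure.
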